# Parexel International

Suzhou Connect Biopharmaceuticals Ltd.  
CBP-201-WW003

Statistical Analysis Plan

Protein	NA
Specific Gravity	NA
Urobilinogen	NA
Microscopic Analysis if abnormal	NA

## 6.5 Appendix E: CTCAE V5.0 Toxicity Grading for Laboratory Parameters

CTCAE v5.0 SOC	CTCAE v5.0 Term	Laboratory Parameter	Grade 1	Grade 2	Grade 3	Grade 4
Blood and lymphatic system disorders	Anemia	Hemoglobin (Hgb)	Hemoglobin (Hgb) <LLN - 10.0 g/dL; <LLN - 6.2 mmol/L; <LLN - 100 g/L	Hgb <10.0 - 8.0 g/dL; <6.2 - 4.9 mmol/L; <100 - 80g/L	Hgb <8.0 g/dL; <4.9 mmol/L; <80 g/L; transfusion indicated	
	Eosinophilia	Eosinophils in the blood	>ULN and >Baseline	-		-
	Leukocytosis	White blood cells in the blood	-	-	>100,000/mm 	
Investigations	Activated partial thromboplastin time prolonged	Partial Thromboplastin Time (PTT)	>ULN - 1.5 x ULN	>1.5 - 2.5 x ULN	>2.5 x ULN; bleeding	-
	Alanine aminotransferase increased	Alanine aminotransferase (ALT or SGPT) in the blood specimen	>ULN - 3.0 x ULN if baseline was normal; 1.5 - 3.0 x baseline if baseline was abnormal	>3.0 - 5.0 x ULN if baseline was normal; >3.0 - 5.0 x baseline if baseline was abnormal	>5.0 - 20.0 x ULN if baseline was normal; >5.0 - 20.0 x baseline if baseline was abnormal	>20.0 x ULN if baseline was normal; >20.0 x baseline if baseline was abnormal
	Alkaline phosphatase increased	Alkaline phosphatase in a blood specimen	>ULN - 2.5 x ULN if baseline was normal; 2.0 - 2.5 x baseline if baseline was abnormal	>2.5 - 5.0 x ULN if baseline was normal; >2.5 - 5.0 x baseline if baseline was abnormal	>5.0 - 20.0 x ULN if baseline was normal; >5.0 - 20.0 x baseline if baseline was abnormal	>20.0 x ULN if baseline was normal; >20.0 x baseline if baseline was abnormal

# Parexel International

Suzhou Connect Biopharmaceuticals Ltd.  
CBP-201-WW003

## Statistical Analysis Plan

	Aspartate aminotransferase increased	Aspartate aminotransferase (AST or SGOT) in a blood specimen	>ULN - 3.0 x ULN if baseline was normal; 1.5 - 3.0 x baseline if baseline was abnormal	>3.0 - 5.0 x ULN if baseline was normal; >3.0 - 5.0 x baseline if baseline was abnormal	>5.0 - 20.0 x ULN if baseline was normal; >5.0 - 20.0 x baseline if baseline was abnormal	>20.0 x ULN if baseline was normal; >20.0 x baseline if baseline was abnormal
	Blood bicarbonate decreased	Bicarbonate in a venous blood specimen	<LLN and no intervention initiated	-	-	-
	Blood bilirubin increased	Bilirubin in a blood specimen	>ULN - 1.5 x ULN if baseline was normal; > 1.0 - 1.5 x baseline if baseline was abnormal	>1.5 - 3.0 x ULN if baseline was normal; >1.5 - 3.0 x baseline if baseline was abnormal	>3.0 - 10.0 x ULN if baseline was normal; >3.0 - 10.0 x baseline if baseline was abnormal	>10.0 x ULN if baseline was normal; >10.0 x baseline if baseline was abnormal
	Blood lactate dehydrogenase increased	Lactate dehydrogenase in the blood specimen	>ULN	-	-	-
	Cholesterol high	Cholesterol in a blood specimen	>ULN - 300 mg/dL; >ULN - 7.75 mmol/L	>300 - 400 mg/dL; >7.75 - 10.34 mmol/L	>400 - 500 mg/dL; >10.34 - 12.92 mmol/L	>500 mg/dL; >12.92 mmol/L
	CPK increased	Creatine phosphokinase in a blood specimen	>ULN - 2.5 x ULN	>2.5 x ULN - 5 x ULN	>5 x ULN - 10 x ULN	>10 x ULN
	Creatinine increased	Creatinine in a biological specimen	>ULN - 1.5 x ULN	>1.5 - 3.0 x baseline; >1.5 - 3.0 x ULN	>3.0 x baseline; >3.0 - 6.0 x ULN	>6.0 x ULN

	GGT increased	Gamma-glutamyltransferase in the blood specimen	>ULN - 2.5 x ULN if baseline was normal; 2.0 - 2.5 x baseline if baseline was abnormal	>2.5 - 5.0 x ULN if baseline was normal; >2.5 - 5.0 x baseline if baseline was abnormal	>5.0 - 20.0 x ULN if baseline was normal; >5.0 - 20.0 x baseline if baseline was abnormal	>20.0 x ULN if baseline was normal; >20.0 x baseline if baseline was abnormal
	Hemoglobin increased	Hemoglobin	Increase in >0 - 2 g/dL	Increase in >2 - 4 g/dL	Increase in >4 g/dL	-
	INR increased	INR	>1.2 - 1.5; >1 - 1.5 x baseline if on anticoagulation; monitoring only indicated	>1.5 - 2.5; >1.5 - 2.5 x baseline if on anticoagulation; dose adjustment indicated	>2.5; >2.5 x baseline if on anticoagulation; bleeding	-
	Lipase increased	Lipase in a biological specimen	>ULN - 1.5 x ULN	>1.5 - 2.0 x ULN; >2.0 - 5.0 x ULN and asymptomatic	>2.0 - 5.0 x ULN with signs or symptoms; >5.0 x ULN and asymptomatic	>5.0 x ULN and with signs or symptoms
	Lymphocyte count decreased	Lymphocytes in a blood specimen	<LLN - 800/mm  ; <LLN - 0.8 x 10  /L	<800 - 500/mm  ; <0.8 - 0.5 x 10  /L	<500 - 200/mm  ; <0.5 - 0.2 x 10  /L	<200/mm  ; <0.2 x 10  /L
	Lymphocyte count increased	Lymphocytes in the blood	-	>4000/mm  - 20,000/mm 	>20,000/mm 	-
	Neutrophil count decreased	Neutrophils in a blood specimen	<LLN - 1500/mm  ; <LLN - 1.5 x 10  /L	<1500 - 1000/mm  ; <1.5 - 1.0 x 10  /L	<1000 - 500/mm  ; <1.0 - 0.5 x 10  /L	<500/mm  ; <0.5 x 10  /L

	Pancreatic enzymes decreased	Pancreatic enzymes in a biological specimen	<LLN and asymptomatic			
	Platelet count decreased	Platelets in a blood specimen	<LLN - 75,000/mm  ; <LLN - 75.0 x 10  /L	<75,000 - 50,000/mm  ; <75.0 - 50.0 x 10  /L	<50,000 - 25,000/mm  ; <50.0 - 25.0 x 10  /L	<25,000/mm  ; <25.0 x 10  /L
	Serum amylase increased	Amylase in a serum specimen	>ULN - 1.5 x ULN	>1.5 - 2.0 x ULN; >2.0 - 5.0 x ULN and asymptomatic	>2.0 - 5.0 x ULN with signs or symptoms; >5.0 x ULN and asymptomatic	>5.0 x ULN and with signs or symptoms
	White blood cell decreased	White blood cells in a blood specimen	<LLN - 3000/mm  ; <LLN - 3.0 x 10  /L	<3000 - 2000/mm  ; <3.0 - 2.0 x 10  /L	<2000 - 1000/mm  ; <2.0 - 1.0 x 10  /L	<1000/mm  ; <1.0 x 10  /L
Metabolism and nutrition disorders	Acidosis	Acidity of the blood	pH <normal, but >=7.3	-	pH <7.3	
	Alkalosis	Alkalinity of the blood	pH >normal, but <=7.5	-	pH >7.5	
	Hypercalcemia	Calcium (corrected for albumin) in blood	Corrected serum calcium of >ULN - 11.5 mg/dL; >ULN - 2.9 mmol/L; Ionized calcium >ULN - 1.5 mmol/L	Corrected serum calcium of >11.5 - 12.5 mg/dL; >2.9 - 3.1 mmol/L; Ionized calcium >1.5 - 1.6 mmol/L; symptomatic	Corrected serum calcium of >12.5 - 13.5 mg/dL; >3.1 - 3.4 mmol/L; Ionized calcium >1.6 - 1.8 mmol/L; hospitalization indicated	Corrected serum calcium of >13.5 mg/dL; >3.4 mmol/L; Ionized calcium >1.8 mmol/L; life-threatening consequences

	Hyperkalemia	Potassium in the blood	>ULN - 5.5 mmol/L	>5.5 - 6.0 mmol/L; intervention initiated	>6.0 - 7.0 mmol/L; hospitalization indicated	>7.0 mmol/L; life-threatening consequences
	Hypermagnesemia	Magnesium in the blood	>ULN - 3.0 mg/dL; >ULN - 1.23 mmol/L	-	>3.0 - 8.0 mg/dL; >1.23 - 3.30 mmol/L	>8.0 mg/dL; >3.30 mmol/L; life-threatening consequences
	Hypernatremia	Sodium in the blood	>ULN - 150 mmol/L	>150 - 155 mmol/L; intervention initiated	>155 - 160 mmol/L; hospitalization indicated	>160 mmol/L; life-threatening consequences
	Hypertriglyceridemia	Triglyceride concentration in the blood	150 mg/dL - 300 mg/dL; 1.71 mmol/L - 3.42 mmol/L	>300 mg/dL - 500 mg/dL; >3.42 mmol/L - 5.7 mmol/L	>500 mg/dL - 1000 mg/dL; >5.7 mmol/L - 11.4 mmol/L	>1000 mg/dL; >11.4 mmol/L; life-threatening consequences
	Hyperuricemia	Uric acid	>ULN without physiologic consequences	-	>ULN with physiologic consequences	
	Hypoalbuminemia	Albumin in the blood	<LLN - 3 g/dL; <LLN - 30 g/L	<3 - 2 g/dL; <30 - 20 g/L	<2 g/dL; <20 g/L	
	Hypocalcemia	Calcium (corrected for albumin) in the blood	Corrected serum calcium of <LLN - 8.0 mg/dL; <LLN - 2.0 mmol/L; Ionized calcium <LLN - 1.0 mmol/L	Corrected serum calcium of <8.0 - 7.0 mg/dL; <2.0 - 1.75 mmol/L; Ionized calcium <1.0 - 0.9 mmol/L; symptomatic	Corrected serum calcium of <7.0 - 6.0 mg/dL; <1.75 - 1.5 mmol/L; Ionized calcium <0.9 - 0.8 mmol/L; hospitalization indicated	Corrected serum calcium of <6.0 mg/dL; <1.5 mmol/L; Ionized calcium <0.8 mmol/L; life-threatening consequences

Parexel International

Suzhou Connect Biopharmaceuticals Ltd.  
CBP-201-WW003

Statistical Analysis Plan

	Hypoglycemia	Glucose in the blood	<LLN - 55 mg/dL; <LLN - 3.0 mmol/L	<55 - 40 mg/dL; <3.0 - 2.2 mmol/L	<40 - 30 mg/dL; <2.2 - 1.7 mmol/L	<30 mg/dL; <1.7 mmol/L; lifethreatening consequences; seizures
	Hypokalemia	Potassium in the blood	<LLN - 3.0 mmol/L	Symptomatic with <LLN - 3.0 mmol/L; intervention indicated	<3.0 - 2.5 mmol/L; hospitalization indicated	<2.5 mmol/L; life-threatening consequences
	Hypomagnesemia	Magnesium in the blood	<LLN - 1.2 mg/dL; <LLN - 0.5 mmol/L	<1.2 - 0.9 mg/dL; <0.5 - 0.4 mmol/L	<0.9 - 0.7 mg/dL; <0.4 - 0.3 mmol/L	<0.7 mg/dL; <0.3 mmol/L; lifethreatening consequences
	Hyponatremia	Sodium in the blood	<LLN - 130 mmol/L	125-129 mmol/L and asymptomatic	125-129 mmol/L symptomatic; 120-124 mmol/L regardless of symptoms	<120 mmol/L; life-threatening consequences
Renal and urinary disorders	Chronic kidney disease	eGFR or CrCl or Urine protein	eGFR (estimated Glomerular Filtration Rate) or CrCl (creatinine clearance) <LLN - 60 ml/min/1.73 m  or proteinuria 2+ present; urine	eGFR or CrCl 59 - 30 ml/min/1.73 m 	eGFR or CrCl 29 - 15 ml/min/1.73 m 	eGFR or CrCl <15 ml/min/1.73 m  ; dialysis or renal transplant indicated

TP-GDO-WW-016-08

CONFIDENTIAL

Effective Date: 26 Nov 19

Related to: SOP-GDO-WW-019

Project Document Version No. 2.0

Project Document Effective Date: Date of last signature

Page 51 of 52

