### 4.2 Definitions

#### Age at Baseline

Age will be calculated using the date of birth and date of the baseline visit as below:

Integer part of [(Date of Baseline Visit – Date of Birth) / 365.25]

Baseline

Unless otherwise specified, baseline is defined as the last non-missing value prior to the first dose of study drug. If time is not collected but the assessment is performed on the same day as the first dose of study drug, it would be considered as baseline.

Baseline Week

For weekly average analysis, baseline week is defined as 7 days prior to the baseline visit (Study day ranges from -7 to -1).

Change from Baseline

Change from baseline is defined as post-baseline value minus baseline value.

Study Day 1

Study day 1 is defined as the date of randomization for untreated randomized subjects or the date of first dose for treated subjects.

Study Day

Study Day will be calculated relative to the date of randomization for untreated randomized subjects and relative to the date of first dose for treated subjects.

If event is prior to the first dose, then study day is calculated as:

$$\text{Date of Event} - \text{Date of First Dose}$$

If event is after the first dose, then study day is calculated as:

$$\text{Date of Event} - \text{Date of First Dose} + 1$$

Duration of Treatment

Duration of Treatment (days) will be calculated as:

$$\text{Last Date of Dose} - \text{First Date of Dose} + 1$$

Treatment-Emergent Adverse Events

Treatment-emergent adverse events are defined as any adverse events occurred or worsen during the treatment-period, whether considered related to the treatment.

Where the AE start date is missing, adverse events will be assumed to be treatment-emergent, unless there is clear evidence (through comparison of partial dates) to suggest that the adverse event started prior to the first dose of study treatment.

Prior and Concomitant Medication

Prior and concomitant medication is defined as any medications that started before the first dose of study drug and stops on or after the first dose of study drug.

Prior Medication

Prior medication is defined as any medications that started and stopped before the first dose of study drug.

Concomitant Medication

Concomitant medication is defined as any medications that started on or after the first dose of study drug.

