#### 4.12.4 Clinical Laboratory Evaluation

All laboratory values will be reported and summarized using standard international (SI) units ([Appendix D – Laboratory SI U](#)). CTCAE v5.0 will be used for the laboratory toxicity grade ([Appendix E: CTCAE V5.0 Toxicity Grading for Laboratory Parameters](#)).

The following central laboratory tests will be summarized:

- Hematology: red blood cell count, hemoglobin level, hematocrit level, white blood cell count with differential, and platelet count
- Serum Chemistry: blood urea nitrogen (BUN), creatinine, uric acid, total bilirubin, sodium, potassium, calcium, chloride, bicarbonate, alkaline phosphatase (ALP), aspartate aminotransferase (AST), alanine aminotransferase (ALT), lactate dehydrogenase (LDH), gamma-glutamyltransferase (GGT), creatine phosphokinase (CPK), albumin, total protein, total cholesterol, triglycerides, C-reactive protein (CRP), and glucose
- Urinalysis: pH, protein, glucose, ketones, bilirubin, blood (hemoglobin), urobilinogen, nitrites, leukocytes, and specific gravity; microscopic analysis if abnormal

Continuous test results for each parameter and changes from baseline will be summarized at each visit by treatment and overall using descriptive statistics. Categorical test results for each parameter will be summarized at each visit by treatment and overall using frequencies and percentages. Shift of laboratory toxicity grade from baseline to each post-baseline visit will be summarized by treatment and overall. By-subject listings of laboratory parameters will also be provided.

Laboratory values will be listed by subject and study time point including changes from baseline, where available. All values outside the clinical reference ranges will be flagged in the data listings. The abnormal values will be flagged with 'L' for values below the lower limit of the clinical reference range and 'H' for values above the upper limit of the clinical reference range and included in the listings.

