#### **4.15 Changes in the Conduct of the Study or Planned Analysis**

Enrollment of Sponsor's Phase 2 trial evaluating CBP-201 in chronic rhinosinusitis with nasal polyps, which commenced in June 2021, has faced challenges due to the macroenvironment -- namely ongoing impact of COVID and the current Russia-Ukraine conflict throughout [Eastern] Europe.

Therefore, the Sponsor has made the decision to terminate this trial early, and the planned analyses have been changed to focus on safety assessments.

For the efficacy endpoints, only descriptive summary statistics will be provided for the co-primary efficacy assessments. No formal hypotheses will be tested due to the small sample size. No sensitivity or subgroup analyses will be performed. All other efficacy assessments will be listed except percentage of maxillary sinus volume occupied by disease on CT and Lund-Mackay Computed Tomography scores.

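### SAP Appendix E grades a hemoglobin rise from just above zero, with no upper-limit condition and no stated reference point; read as change from baseline, noise alone would put about 43% to 47% of patients at Grade 1 at each visit

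*SAP*

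**What the plan says.** SAP Appendix E has a row for increased hemoglobin. Grade 1 is "Increase in >0 - 2 g/dL", Grade 2 is "Increase in >2 - 4 g/dL", and Grade 3 is any larger increase. No cell mentions ULN or names the value from which the increase is counted. The row is in g/dL only, while SAP Appendix D sets g/L as the reporting unit for hemoglobin.

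Other rows in the appendix set a limit. Eosinophilia Grade 1 is ">ULN and >Baseline". ALT, AST, ALP, bilirubin and GGT start Grade 1 above ULN when baseline is normal; LDH, CPK and creatinine start it above ULN without a baseline clause. Hemoglobin is also graded downwards as anemia, from "Hemoglobin (Hgb) <LLN - 10.0 g/dL".

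SAP 4.12.4 puts the appendix to use: "CTCAE v5.0 will be used for the laboratory toxicity grade", and "Shift of laboratory toxicity grade from baseline to each post-baseline visit will be summarized by treatment and overall". After the early termination, SAP 4.15 says that "the planned analyses have been changed to focus on safety assessments". It does not withdraw the laboratory shift tables.

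**The concern.** A toxicity grade in a shift table should mark movement into abnormality. This row has neither a limit nor a minimum rise. If the increase is counted from baseline, a patient who goes from 140 to 141 g/L, an assumed within-range pair, moves from Grade 0 to Grade 1. Every patient is also Grade 0 at baseline by construction, including one who already exceeds ULN; if that patient then stays level, the grade remains 0. The grade would follow the sign of a small difference, not abnormality.

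What is at stake is the readability of one safety table in a trial whose report is now mainly about safety. A large Grade 1 count in every arm, placebo included, would consist mostly of day-to-day and assay variation. With few patients, chance differences between arms in that count could look like a finding.

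**Working it through.** The documents give no hemoglobin variability and no expected share graded, so there is no plan figure to reproduce. The check asks what the row yields when nothing happens.

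**Inputs from the documents**
- Grade bands: above 0 to 2, above 2 to 4, and above 4 g/dL (SAP Appendix E). At 10 g/L per g/dL the cut-offs are 20 and 40 g/L.
- Change: "Change from baseline is defined as post-baseline value minus baseline value" (SAP 4.2). Applying this to the row is a reading; the row itself does not say so.
- Planned size: 49 per arm (SAP 4.14), used only for scale.

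**Assumptions**
- Within-patient SD *s* of 2 to 8 g/L, values rounded to 1 g/L, no true change.
- For the last column of the table: mean 140 g/L, between-patient SD 10 g/L, and ULN at the 97.5th percentile, that is 140 + 1.96 × √(10² + *s*²). For *s* = 5 this is 140 + 1.96 × 11.18 = 161.9 g/L.

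**Formula.** With no true change, post-baseline minus baseline is symmetric about zero, so

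P(rise > 0) = (1 − P(tie)) / 2.

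The difference has SD *s*√2, so with rounding to 1 g/L, P(tie) ≈ 1 / (2*s*√π). For *s* = 2 this is 1 / 7.09 = 0.141; for *s* = 8 it is 1 / 28.36 = 0.035. Grade 1 is P(rise > 0) less the share that rises by more than 20 g/L.

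**Results** (simulation, 400,000 patients, one post-baseline visit)

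| *s* (g/L) | P(tie) | (1 − tie)/2 | Grade 2 or higher | Grade 1 | Grade 1 of 49 | Graded if also above ULN |
|---|---|---|---|---|---|---|
| 2 | 0.139 | 0.431 | 0.000 | 0.430 | 21.1 | 1.5% |
| 3 | 0.093 | 0.454 | 0.000 | 0.452 | 22.1 | 1.6% |
| 4 | 0.070 | 0.465 | 0.000 | 0.464 | 22.7 | 1.6% |
| 5 | 0.056 | 0.472 | 0.002 | 0.469 | 23.0 | 2.0% |
| 6 | 0.047 | 0.477 | 0.008 | 0.469 | 23.0 | 2.1% |
| 8 | 0.035 | 0.483 | 0.036 | 0.446 | 21.9 | 2.0% |

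Small gaps between the third column and the sum of the next two are simulation error and rounding.

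The Grade 1 share hardly depends on *s*, because it is one half less half the ties and a small upper tail. It does depend on the mean being stable: a true mean fall of 1 g/L lowers it to about 30% to 43%, but that is no longer noise alone.

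**The case against.** The strongest objection is that the row names no reference point. If the increase is counted from ULN, most of the problem disappears, since few values exceed that limit. This stands. The 43% to 47% is conditional on the baseline reading, and a reader should not infer that nearly half the patients will certainly be graded. What is certain is that the row does not settle the matter.

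Second, the appendix carries the CTCAE v5.0 title, and the row may simply reproduce that standard. This cannot be checked from the documents, so the point does not claim a transcription error. Nor does the appendix have a uniform ULN rule: triglycerides start at 150 mg/dL, lymphocyte increase at 4000/mm³, INR at 1.2, and creatinine Grade 2 includes a multiple of baseline. Those rows still set a threshold or a minimum proportional rise; the lowest band of the hemoglobin row sets neither. The INR row's baseline arm comes closest, but it applies only to patients on anticoagulation.

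Third, a reader might infer that real elevations would be hidden. The documents do not support that. SAP 4.12.4 also plans actual values and changes from baseline at each visit by arm, and flags every value above the reference range in the listings. Rises above 2 and 4 g/dL have their own grades.

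Fourth, a reader might accumulate the per-visit share over all post-baseline visits and reach a much larger figure. SAP 4.12.4 plans shifts to each visit, not a worst post-baseline shift, so that figure would match no planned output; it would also assume complete follow-up in a trial that stopped early.

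Finally, no test or endpoint uses this row. Hemoglobin is not an adverse event of special interest (SAP 4.12.3), and reporting a laboratory value as an adverse event rests on the investigator's judgement (Protocol 7.6 and 8.2). This stands and keeps the point minor.

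**Conclusion.** The point holds as a minor defect. The row lacks a reference point and a ULN condition. If it is applied as change from baseline, the hemoglobin shift table would place about 43% to 47% of patients at Grade 1 at each visit with no drug effect, or about 21 to 23 of 49 per arm at the planned size. The actual arms are smaller, since SAP 4.15 cites a small sample. The within-patient SD of 2 to 8 g/L, the 1 g/L precision and the stable mean are assumptions.

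A reader might infer that this favours one arm. It does not: noise acts on all arms alike, so the systematic effect is dilution of one descriptive table, not bias.

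**What to change.** Amend the hemoglobin row of SAP Appendix E, or add a footnote to it:

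- State the reference point for the increase.
- Assign a grade only when the post-baseline value is above ULN. Grade by the rise above ULN, or above baseline if baseline already exceeds ULN.
- Give the cut-offs in g/L as well (20 and 40), to match Appendix D.
- Footnote that the row departs from its literal wording under the CTCAE heading.

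Under the assumptions above, noise would then grade about 2% of patients per visit. Separate tables for high and low hemoglobin shifts are optional; the appendix already lists the two as distinct terms.

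The cost is one row and one line of derivation code. The downside is the departure from the row's literal wording, and fewer low-grade entries than that wording would give.

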# Parexel International

Suzhou Connect Biopharmaceuticals Ltd.

CBP-201-WW003

## Statistical Analysis Plan

			protein/creatinine >0.5			
	Proteinuria	Urine protein	1+ proteinuria; urinary protein ≥ULN -	2+ and 3+ proteinuria; urinary protein 1.0 - <3.5 g/24 hrs	Urinary protein ≥3.5 g/24 hrs; 4+ proteinuria	-

TP-GDO-WW-016-08

Effective Date: 26 Nov 19

Related to: SOP-GDO-WW-019

